9.4. Statistical Analyses

The SAP will be finalized prior to the data base lock (DBL) of the primary analysis, and it will include a more technical and detailed description of the statistical analyses described in this section. This section is a summary of the planned statistical analyses of the most important endpoints including primary and key secondary endpoints. Due to cease of enrollment and limited sample size, some endpoints might not be summarized and will only be provided in listings. More details can be found in the SAP.

9.4.1. General Considerations

Analysis populations are defined in Section 9.3.

Primary and final analyses are defined in Sections 9.5.1 and 9.5.2.

No formal statistical testing of safety or immunogenicity data is planned. Safety and immunogenicity will be summarized with descriptive statistics by group and overall. Safety and immunogenicity analyses may also be performed by stage of pregnancy (16-27 weeks, 28-38 weeks), administration of booster (Yes, No), SARS-CoV-2 baseline serostatus (Positive, Negative) at which the vaccine was administered and by actual vaccine history within each group.

For adult participants, all safety analyses will be performed on the FAS-A and immunogenicity analyses will be performed on the PPI-A by group and overall.

For neonates/infants, safety analyses will be performed on the FAS-NVN and immunogenicity analyses will be performed on the PPI-NVN set by group and overall.

The number and percentage of participants screened, enrolled, vaccinated, received a booster vaccine and completed follow-up will be summarized by group and overall.

Baseline is considered as the last available assessment before vaccination. For neonates baseline is value at birth.

9.4.2. Primary/Secondary Endpoint(s)

Immunogenicity Endpoints

Descriptive statistics (geometric mean and confidence intervals, or median and interquartile range Q1-Q3, as appropriate) will be calculated by group and overall for immunologic parameters for all available time points for adult participants receiving Ad26.COV2.S during the 2nd and/or 3rd trimester of pregnancy. Descriptive statistics will also be presented for neonates/infants of adult participants who have received Ad26.COV2.S during the 2nd and/or 3rd trimester of pregnancy by group and overall. Several definitions of serological response will be applied (fold increases in GMC [S-ELISA] or GMT [VNA]). Graphical representations of immunologic parameters will be prepared as applicable. Frequency tabulations will be calculated for discrete (qualitative) immunologic parameters, as applicable.

The impact of baseline characteristics on the humoral responses may be explored graphically or with descriptive statistics by group and overall.

For adult participants, immunogenicity analyses may also be performed by stage of pregnancy at which the vaccine was administered, SARS-CoV-2 baseline serostatus and by actual vaccine history within each group.

For neonates/infants, analyses may also be performed by the gestational age at the time of vaccine administration, and SARS-CoV-2 baseline serostatus of the adult participant.

Safety Endpoints

No formal statistical testing of safety data is planned. Safety data will be analyzed descriptively by group and overall for adult participants (including pregnancy outcomes: live term birth, live preterm birth, stillbirth, and abortion) and their neonates/infants up to approximately 12 months of age (including normal neonate, term neonate with (and without) complications, preterm neonate with (and without) complications, neonatal infection, respiratory distress, congenital anomalies, neonatal death, low birth weight, and small for gestational age) for all adult participants receiving the Ad26.COV2.S vaccine. Safety data from participants vaccine naïve at study entry who receive a booster may be provided as a separate descriptive analysis by group and overall (further details are available in the SAP).

For adult participants, safety analyses may also be performed by stage of pregnancy at which the vaccine was administered and by SARS-CoV-2 baseline serostatus.

Adverse Events

The verbatim terms used in the eCRF by investigators to identify AEs will be coded using the Medical Dictionary for Regulatory Activities (MedDRA). All reported AEs and events-related reactogenicity diary information will be included in the analysis: solicited local at injection site and systemic AEs with onset after vaccination, and unsolicited AEs with onset after vaccination. For each AE, the percentage of participants who experience at least one occurrence of the given event will be summarized by group and overall separately for adult participants (up to at least 12 months postpartum) and their neonates/infants (up to approximately 12 months of age).

Pregnancy-related AEs throughout pregnancy (including gestational diabetes, gestational hypertension, premature rupture of membranes, premature labor, premature uterine contractions, poor or restricted fetal growth, pre-eclampsia, eclampsia, vaginal or intrauterine hemorrhage [non-exhaustive]) will be assessed and analyzed for adult participants by group and overall. The complete list of preferred terms to be included as pregnancy-related AEs will be provided in the SAP.

For SAEs, suspected AESIs and AEs leading to discontinuation throughout the study (from first vaccination until end of the study [at least 12 postpartum]), the percentage of adult participants who experience at least 1 occurrence of the given event will be summarized by group, overall and by phase including post booster (if applicable). For MAAEs (from vaccination until 6 months after

vaccination or until end of study when leading to study discontinuation), the percentage of adult participants who experience at least 1 occurrence of the given event will be summarized by group and overall. SAEs in the neonates/infants from birth until end of study (approximately 12 months of age) will be assessed by group and overall. MAAEs in the neonates/infants (from birth until 6 months of age or from birth until discontinuation [if MAAE is leading to study discontinuation]) will be assessed by group and overall.

Summaries, listings, datasets, or participant narratives may be provided, as appropriate, for those participants who die, who discontinue vaccine due to an AE, or who experience a severe AE, an SAE, or a suspected AESI by group and overall.

Solicited local (at injection site) and systemic AEs will be summarized descriptively by group and overall. The number and percentages of participants with at least one solicited local (at injection site) or systemic AE will be presented by group and overall. The frequencies by group and overall as well as frequencies according to severity and duration will be described for solicited AEs. Frequencies of unsolicited AEs, separately for all and vaccination-related only, will be presented by System Organ Class and preferred term, while those of solicited AEs will be presented only by preferred term.

Outcomes

Adverse maternal/fetal outcomes and adverse neonatal/infant outcomes will be defined using the Case Definitions for Pregnancy Outcomes for each endpoint.

The frequency and percentage of participants for whom at least one of the indicated adverse outcomes was reported will be summarized by group and overall. For each separate adverse maternal/fetal and adverse neonatal/infant outcome, the number and percentage of participants who experience at least 1 occurrence of the given event will also be tabulated by group and overall.

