If a potential participant does not have HIV viral load and CD4 cell count data in their medical records from the last 6 months, efforts will be made to obtain the necessary data for potential entry into the study. A laboratory result within 6 months of screening does not need to be repeated.

4. Criterion modified per Amendment 4.
 - a. If on medication for a condition, the medication dose must have been stable for at least 4 weeks preceding vaccination.
5. Participant will be included on the basis of physical examination, medical history, and vital signs^a.
6. Criterion modified per Amendment 1.
 - a. Criterion modified per Amendment 4

^a Participants may be enrolled with Grade 1 or Grade 2 toxicity gradings for vital signs measurements per the Investigator's discretion.

- b. Participant will be at 2nd or 3rd trimester of pregnancy, ie, Week 16 to Week 38 of gestation (inclusive), at the time of vaccination, based on ultrasound at the time of screening (or not longer than 10 days prior to vaccination if performed elsewhere).
7. Participant agrees to not donate bone marrow, blood, and blood products from the first study vaccine administration until 3 months after receiving the last dose of study vaccine.
8. Participant must be willing to provide verifiable identification, has means to be contacted and to contact the investigator during the study.
9. Participant must have access to a consistent means of contact either by telephone contact or e-mail/computer.
10. Must be able to read, understand and complete questionnaires in a digital application (ie, The “COVID 19 signs and symptoms surveillance question,” the “SIC” for adults and the “PedSIC” for children); and the reactogenicity diary (adults only).^a
11. Criterion modified per Amendment 4.
 - 11.1 Criterion modified per Amendment 6
 - a. Participant either received their last COVID-19 vaccination with an authorized/licensed COVID-19 vaccine (at least 4 months prior to first study vaccination) or is COVID-19 vaccine naïve.

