9.3. Populations for Analysis Sets

For purposes of analysis, the following populations are defined:

Population	Description
Enrolled Adults	All adult participants who sign the ICF
Full Analysis Set-Adults (FAS-A)	All enrolled adult participants with at least one vaccine administration documented
Full Analysis Set-Non-vaccinated Neonates/Infants (FAS-NVN)	All non-vaccinated neonates/infants (NVN) born to Ad26.COV2.S vaccinated adult participants
Per protocol Immunogenicity-Adults (PPI-A)	All vaccinated adult participants for whom immunogenicity data are available excluding adult participants with major protocol deviations that are expected to impact the immunogenicity outcomes. In addition, samples obtained from participants after SARS-CoV-2 infection occurring after baseline (if applicable) will be excluded from the analysis
Per protocol Immunogenicity- Non-vaccinated Neonates/Infants (PPI-NVN)	All non-vaccinated neonates/infants (NVN) born to Ad26.COV2.S vaccinated adult participants for whom immunogenicity data are available excluding neonates/infants born to participants with major protocol deviations that are expected to impact the immunogenicity outcomes (for example missed vaccinations in the mothers), or neonates/infants with major protocol deviations that are expected to impact the immunogenicity outcomes
The list of major protocol deviations to be excluded from the immunogenicity analyses will be specified in the Major Protocol Deviation Criteria document and/or this list will be reported into the protocol deviation dataset of the clinical database before database lock.	

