10.10. Appendix 10: Symptoms of Coronavirus (US Centers for Disease Control and Prevention)

10.10.1. Appendix 10A: Symptoms of Coronavirus (US Centers for Disease Control and Prevention) in Adults

The following extract shows symptoms of coronavirus infection in adults as listed on the US CDC website dated 09 November 2020 and were still accurate at the time of finalization of this protocol:

(<https://www.cdc.gov/coronavirus/2019-ncov/symptoms-testing/symptoms.html>).

People with COVID-19 have had a wide range of symptoms reported - ranging from mild symptoms to severe illness. Symptoms may appear **2-14 days after exposure to the virus**. People with these symptoms may have COVID-19:

- Fever or chills
- Cough
- Shortness of breath or difficulty breathing
- Fatigue
- Muscle or body aches
- Headache
- New loss of taste or smell
- Sore throat
- Congestion or runny nose
- Nausea or vomiting
- Diarrhea

10.10.2. Appendix 10B: Symptoms of Coronavirus (US Centers for Disease Control and Prevention) in Neonates

The following extract shows symptoms of coronavirus infection in neonates as listed on the US CDC website dated 23 October 2020 and were still accurate at the time of finalization of this protocol:

(<https://www.cdc.gov/coronavirus/2019-ncov/hcp/caring-for-newborns.html>)

Note: Current evidence suggests that SARS-CoV-2 infections in neonates are uncommon. If neonates do become infected, the majority have either asymptomatic infections or mild disease (ie, do not require respiratory support), and they recover. Severe illness in neonates, including illness requiring mechanical ventilation, has been reported but appears to be rare. Neonates with underlying medical conditions and preterm infants (<37 weeks gestational age) may be at higher risk of severe illness from COVID-19.

Reported signs among neonates with SARS-CoV-2 infection include:

- Fever
- Lethargy
- Rhinorrhea
- Cough
- Tachypnea
- Increased work of breathing
- Vomiting
- Diarrhea
- Poor feeding

The extent to which SARS-CoV-2 infection contributed to the reported signs of infection and complications is unclear, as many of these findings are common in term and preterm infants for other reasons (eg, transient tachypnea of the neonate, neonatal respiratory distress syndrome).

10.10.3. Appendix 10C: Symptoms of Coronavirus (US Centers for Disease Control and Prevention) in Children

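### Preterm birth, preterm labour and abortion are to be reported as percentages of all vaccinated women, including those vaccinated too late to have them, so these percentages run low and shift with gestational mix

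*Protocol*

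**What the plan says.** Under Outcomes, protocol Section 9.4.2 plans to summarise "The frequency and percentage of participants for whom at least one of the indicated adverse outcomes was reported", by group and overall. The same form of table is planned for each separate maternal, fetal, neonatal and infant outcome. That sentence names no denominator, but three other statements supply one:

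- Section 9.4.1: "For adult participants, all safety analyses will be performed on the FAS-A".
- Section 9.3 defines the FAS-A as "All enrolled adult participants with at least one vaccine administration documented".
- Section 9.4.2, Safety Endpoints, lists "pregnancy outcomes: live term birth, live preterm birth, stillbirth, and abortion" and analyses them "for all adult participants receiving the Ad26.COV2.S vaccine".

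Inclusion criterion 6 (Section 5.1) admits women in the 2nd or 3rd trimester, "ie, Week 16 to Week 38 of gestation (inclusive), at the time of vaccination". The only preterm cut-off in the protocol is in Appendix 10.10.2: "preterm infants (<37 weeks gestational age". The outcomes themselves are defined by external case definitions, and the protocol gives no gestational limit for abortion.

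Analysis by stage of pregnancy (16-27 and 28-38 weeks) is optional in Sections 9.4.1 and 9.4.2. The mix is controlled only by a goal of about 25% of participants per trimester in each group (Section 4.1).

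**The concern.** A percentage estimates a risk only if everyone in the denominator could have had the event. A woman vaccinated at 37 or 38 weeks has already passed the point at which delivery would be preterm. A woman vaccinated beyond the limit for abortion can no longer have one. Both stay in the denominator and contribute no events.

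Section 4.1 says that there is no placebo group. A reader can therefore judge the pregnancy-outcome percentages only against outside rates or between vaccination-history groups. Against outside rates, the preterm and abortion percentages would look better than they should with no vaccine effect at all. Between groups, the one with more late entrants would look safer.

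**Working it through.** **The plan's own figure.** Section 9.2 gives upper 95% limits for zero events among all those vaccinated: 8.8%, 6%, 3% and 1.5% for N = 40, 60, 120 and 240. The exact two-sided limit, 1 − 0.025^(1/N), gives 8.81%, 5.96%, 3.03% and 1.53%, so these reproduce. They are general AE figures with all N at risk. The protocol states no expected preterm or abortion rate for this trial.

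**Inputs.** Entry from Week 16 to 38 (Section 5.1); strata 16-27 and 28-38 weeks (Section 9.4.1); preterm below 37 weeks (Appendix 10.10.2); a later-stratum share between about 25% and 75%, implied by the 25% goal (Section 4.1). The 8.9% is the external baseline preterm rate cited in Section 2, used only for illustration. Assumption: entry is uniform over completed weeks within each stratum.

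**Preterm birth.** Weeks 37 and 38 are 2 of the 11 weeks from 28 to 38, so 2/11 = 18.2% of the later stratum is not at risk. Overall share not at risk = later-stratum share × 2/11. Reported percentage = 8.9% × (1 − share not at risk).

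| Later-stratum share | Not at risk | 8.9% is reported as |
|---|---|---|
| 25% | 4.5% | 8.5% |
| 50% | 9.1% | 8.1% |
| 75% | 13.6% | 7.7% |
| 28-38 week stratum alone | 18.2% | 7.3% |

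If Week 38 is taken to end at 38 weeks 0 days, the fraction is 1/10. The overall shares are then 2.5%, 5.0% and 7.5%, and the reported figures are 8.9% × 0.975 = 8.7%, × 0.95 = 8.5% and × 0.925 = 8.2%.

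**Abortion.** For an assumed cut-off c of 20, 22, 24 or 28 weeks, the share at risk = (1 − later-stratum share) × (c − 16)/12.

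- 25% in the later stratum: 25%, 37.5%, 50%, 75% at risk.
- 75% in the later stratum: 8.3%, 12.5%, 16.7%, 25% at risk.

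The all-vaccinated percentage is thus too small by a factor between 1/0.75 = 1.3 and 1/0.083 = 12. Out of the planned target of 240, the women at risk would number 180 down to 20. Zero abortions would then support an upper limit of 1 − 0.025^(1/180) = 2.0% up to 1 − 0.025^(1/20) = 16.8%, not 1.5%.

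**Shortened time at risk.** A woman vaccinated at 36 weeks is at risk for less time than one vaccinated at 20 weeks. As a sensitivity check, let the weekly preterm hazard double every 1 to 4 weeks, scaled to 8.9% from week 20 (assumed shapes).

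| Later-stratum share | All vaccinated | Vaccinated before 37 weeks only |
|---|---|---|
| 25% | 7.5-8.3% | 7.9-8.7% |
| 50% | 6.4-7.7% | 7.0-8.5% |
| 75% | 5.3-7.1% | 6.1-8.2% |

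Removing the women with no risk recovers only part of the gap, so a display by stage is needed as well.

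**The case against.** The strongest reply is that the denominator is inferred. The Outcomes sentence does not name it, Section 9.4.1 fixes an analysis set rather than a table denominator, and the SAP, which is not available here, could restrict the percentage to women at risk. It is true that the protocol does not rule this out in so many words. But Section 9.4.2 says that pregnancy outcomes, with preterm birth and abortion named, are analysed for all women who received the vaccine. Followed as written, that gives an all-vaccinated percentage.

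Second, the effect on preterm birth is small. From the women with no risk alone it is 8.9 − 8.5 = 0.4 to 8.9 − 7.7 = 1.2 points. Enrolment has stopped, and the Amendment 7 rationale says that the numbers for the interim analyses (120 and 240) will not be reached. At N = 120 one woman is 1/120 = 0.8 points, and the 95% half-width at 8.9% is 1.96 × √(0.089 × 0.911/120) = 5.1 points. Section 9.4 adds that some endpoints may only be listed. This stands, and it limits the practical weight of the point.

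Third, no hypothesis is tested, and Section 9 plans no comparison with background rates. This also stands: the risk lies in how the percentages are read, not in a faulty test.

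Fourth, the by-stage analysis could separate the mix. In part it could, but it is optional, and its 28-38 week stratum still contains the women vaccinated at 37-38 weeks.

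**Conclusion.** The point holds for preterm birth, preterm labour, preterm neonate and abortion. As written, the plan counts women who cannot have these outcomes, so the percentages run low and depend on gestational mix. For preterm birth the shift is modest: 8.9% reads as 8.5% to 7.7%, or 7.3% in the 28-38 week stratum, under uniform entry. For abortion it is larger, but its size rests on assumed cut-offs. Preterm labour is included on the assumption that the listed premature labour carries the same 37-week limit.

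A reader might infer that pregnancy outcomes in general are biased low. The documents do not support that. Stillbirth, pre-eclampsia and similar outcomes remain possible after vaccination at Week 38, and the term-birth percentage is pushed up. Section 9.4.2 lists premature rupture of membranes with no gestational limit, so zero risk at 37-38 weeks cannot be claimed for it. Nor can one say that no third-trimester entrant is at risk of abortion, because no limit is given. Finally, a before-37-weeks denominator does not make the rates free of gestational mix, since time at risk still differs.

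**What to change.** In Section 9.4.2, and in the SAP tables that follow from it:

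- Report preterm birth and preterm labour among women vaccinated before 37 weeks, and preterm neonate among their infants.
- State the gestational limit for abortion from the case definition, and report abortion among women vaccinated before it.
- Keep the percentage of the full FAS-A (FAS-NVN for infants) as a supportive figure.
- Make the display of these outcomes by stage of pregnancy at vaccination firm, to show the effect of shortened time at risk.

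The cost is a few sentences and revised table denominators. Gestational age at vaccination is already established by ultrasound for eligibility, so no new data or visits are needed. The downside is slightly smaller denominators and slightly less favourable percentages for preterm outcomes; for abortion both changes may be larger.

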9.4.3. Exploratory Endpoint(s)

Transfer of maternal humoral immunity to the infant will be assessed, including:

- levels of maternal IgA and/or other Ig subtypes against SARS-CoV-2 in colostrum and breast milk within 1 week postpartum and at 6 weeks postpartum (Day 43 PP follow-up visit), respectively, if feasible, in a subset of participants who had received Ad26.COV2.S vaccine during the 2nd and/or 3rd trimester of pregnancy. Levels of maternal IgA and/or other Ig subtypes against SARS-CoV-2 will also be assessed in colostrum and/or breast milk, if feasible, at the time of booster vaccination and 28 days post booster vaccination, in participants who were vaccine naïve at study entry and receive a booster after pregnancy completion.
- levels of antibodies in peripheral blood from adult participants and cord blood at the time of delivery. Serological response as measured ELISA will be assessed using GMCs. The GMR (ratio of immunologic parameters between blood and cord blood at time of delivery) will be calculated together with confidence intervals. Additional characterizations will be described in the SAP.

Cellular immune responses induced in participants during the 2nd and/or 3rd trimester of pregnancy after vaccination with Ad26.COV2.S may be further explored using PBMCs obtained on Day 1 (pre-dose), 28 days after vaccination, and at the time of delivery (if feasible), for a subset of participants. With only 1 participant in this subset at the time of writing this Protocol Amendment 7, PBMC sampling may be removed from the study as of Protocol Amendment 7 approval. Analysis will be described in more detail in the SAP.

The correlation between the binding antibody (ELISA) titers and neutralizing antibody (VNA) titers to SARS-CoV-2 will be assessed at selected timepoints using Spearman's rank correlation. Additional details will be provided in the SAP.

The occurrence and severity of COVID-19 infection (asymptomatic and symptomatic) in adult participants or in neonates/infants of participants who have received Ad26.COV2.S during the 2nd and/or 3rd trimester of pregnancy, will be assessed using the case definitions in outlined in Section 10.8.

Plasma and serum derived from whole blood samples will be collected from all participants for retrospective analysis of hematological parameters, including pro- and anti-coagulation factors in the event of a suspected AESI of post-vaccination TTS. The extent to which these coagulation factors correlate with platelet counts assessed at the time, as part of the routine CBC assessment will be determined, and the extent to which levels of these coagulation factors fluctuate pre-and post-vaccination with Ad26.COV2.S may be investigated for research purposes. The platelet count will be performed by a local laboratory or substitute for local laboratory. Blood samples will be collected as detailed in Section 1.3 Schedules of Activities.

Developmental outcomes on the ASQ-3 at 2, 6 and 12 months will be summarized.

